6.1.2. Therapeutic care

Before the introduction of targeted therapies, the median survival time for patients suffering from metastatic renal cell carcinoma was of ten months [11]. The development of targeted therapies, acting both on the mechanisms of angiogenesis and of cell proliferation, has revolutionised the management of renal cell carcinoma [12, 13]. These treatments have led to a progression-free survival with a median value estimated at 11 months and an overall survival of 30 months [14-16].

Sunitinib is a tyrosine kinase inhibitor indicated for the treatment of advanced and/or metastatic renal cell carcinoma. It is currently considered as reference first-line treatment [17]. The pivotal sunitinib vs. INF alpha trial demonstrated a significant improvement in progression-free survival of 11 months under sunitinib versus 5 months under INF α [18]. By virtue of their mechanisms of action, targeted therapies are accompanied by adverse events of variable severity. For sunitinib, it has been shown that certain adverse events are predictive of the patient's response to the treatment [19-22]. Common toxicities have been described for all anti-angiogenic drugs (asthenia, HTN, cardiac toxicity) [23]. In the pivotal sunitinib trial [18], 84% of patients treated with sunitinib presented with at least one grade 3 or 4 adverse event (according to CTCAE version 4.03 of June 2010), whether associated with sunitinib or not. Cardiovascular, dermatological, haematological, gastrointestinal and metabolic disorders require special

surveillance. In the Santorin study (French study of the real-life use of anti-angiogenic drugs) [16], 58% of patients treated with sunitinib presented with at least one grade 3 or 4 adverse event (according to CTCAE version 4.03 of June 2010), whether associated with sunitinib or not. In the EAP "Expanded Access Program" trial [24], 58.8% of patients treated with sunitinib presented with at least one grade 3 or 4 adverse event (according to CTCAE version 4.03 of June 2010), whether associated with sunitinib or not.

The main grade 3 events were hypertension (12.6%), hand and foot syndrome (12.3%), fatigue/asthenia (11.9%), neutropenia (10.6%) and anaemia (9.3%).

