The aim of these calls is to support the patients in the management of their treatment by listening to and advising them, implementing preventive measure and taking actions when deemed necessary; the purpose of these calls is to support patients in the management of their sunitinib treatment.

Call frequency is presented in the following figure:

[figure not shown]

Figure 3. Call frequency

The chosen rate is of:

- For the first two cycles, C1 and C2: 5 calls during the first 5 weeks of each cycle (no call during week 6 as the patients are usually seen in consultation),
- For cycles 3 and 4: 2 calls per cycle on weeks 2 and 4.
(decision by the CS not to make calls on weeks 1, 3 and 5).

These calls will be made for patients treated with Sutent®; in the event of termination of treatment during the follow-up period, the call following termination will close the intervention. In the event of cycle start postponement, the first call made shall be postponed to match the expected organisation (cycles 1 and 2: first call during week 1 of the cycle; cycles 3 and 4: first call during week 2 of the cycle).

Call organisation has been defined in collaboration with the concerned healthcare professionals and based on prior experience of therapy management in oncology. It shall be as follows:

- build the patient's trust by covering various aspects of the disease and/or of side effects;
- patient education to avoid serious adverse events (e.g.: dietary advice, sports exercises, etc.);
- guidance and advice when deemed necessary; for example, this may be to:
 - advise the patient to take medicinal products prescribed upstream by his/her physician,
 - guide the patient towards his/her oncologist or general practitioner or other.

The patients will also be able to contact the call centre nurses at any time during the study. A specific module will enable the nurse to record this type of "unscheduled" call.

The platform will also play a coordination role between patients and healthcare professionals, through the following actions:

- Draw up a call report on the e-CRF. This latter shall include the number of successful calls, along with the actions performed by the call centre for each call, such as: no special action, or self-medication, or consultation request to one of the physicians;

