5. ANALYSIS POPULATION

5.1. *Definition of the analysis populations*

Reported population	All patients reported by the investigators in the non-inclusion register and included in the eCRF.
Safety population	Patients treated with Sunitinib.
Full Analysis Set (FAS) Population	All patients included by the investigating doctors who meet the study eligibility criteria and have received at least one dose of Sunitinib

NB: Where applicable, the two subgroups of patients will in all cases be distinguished in the populations: firstly patients included in the “Call Center” arm (**main interest population**) and patients included in the “standard follow-up” arm (**exploratory population**) set up as part of the initial study design (before amendment No. 3 to the protocol).

Table 3: Population in each analysis

Analyses		Populations analyzed	Analysis subgroup*
Description at inclusion		Safety population	Call Center /standard follow-up
Description of follow-up	All data Main data	Safety population Call Center Safety population Standard follow-up	
Primary objective		Safety population	Number of calls made by the call center*
Secondary objectives	Sunitinib treatment details Planned and unplanned medical procedures Adherence to treatment Objective response rate Telephone calls	Safety population Safety population Safety population FAS population Call Center FAS population	Number of calls made by the call center* Number of calls made by the call center* Number of calls made by the call center* Number of calls made by the call center*
	Patient satisfaction Doctor satisfaction	Call Center FAS population who completed a self-administered satisfaction questionnaire Call Center FAS population for which the Doctors have completed a satisfaction questionnaire	Number of calls made by the call center*
Pharmacovigilance		Safety population	

* cf. definition §5.2.

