5.2. Analysis subgroup

In the assessment of the treatment call center for patient management, analysis of the objectives may be performed overall and according to the number of calls received (two group classification).

In order to define compliance or non-compliance with the intervention, i.e. in order to define the patient as having actually followed the procedure, the scientific committee will define a **minimum number of 7 successful calls out of the planned 14 calls over 4 cycles, with a required minimum of 6 successful calls during the first two treatment cycles, representing at least 3 calls in each of the first two cycles.**

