8.2.4. Analysis of the primary end point

Analysis population: Safety population

The proportion of patients with at least one grade 3 or 4 AE whether or not related to sunitinib, will be estimated.

All of the grades 3 or 4 AEs defined by the 'Common Terminology Criteria for Adverse Events' (CTCAE v4.03 of June 2010), whether or not related to sunitinib, will be included when these occur during the study follow-up period (up to the end of the 4th treatment cycle or until the treatment is stopped if it is discontinued in the 1st, 2nd or 3rd cycle). All of the AEs will be included whether these are declared by the doctor or by the nurse.

The analyses will be performed both on an overall basis and according to the number of calls made by the call center.

Sensitivity analyses:

The sensitivity analyses will be performed:

- Sensitivity to duration of patient treatment: the results will also be expressed as standardized grade 3 or 4 AE rates developed by the patient and reported over the 6 months of treatment. These rates will be defined by each patient as the number of events which occurred/number of treatment months with sunitinib/ 6).

Secondary analysis:

- **The incidence of the main grade 3 or 4 AEs, whether or not related to sunitinib,** will also be presented in these patients according to the MedDRA SOC (System Organ Class) and PT (Preferred Term) classification. Only categories involving at least 2% of patients will be presented.

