8.2.5. Analysis of the secondary end points

8.2.5.1. Sunitinib treatment

Populations analyzed: Safety population

End points:

The analysis of sunitinib treatment methods will be carried out using the following indicators:

▪ **Description of dose reductions**

- Proportion of patients with at least one dose reduction during the period of sunitinib treatment;
- Reasons for the dose reduction: Proportion of patients involved on at least one occasion for each of the reasons for a dose reduction;
- Average dose reduction.

▪ **Description of interruptions to treatment**

- Proportion of patients who interrupted sunitinib treatment temporarily during treatment (including declared temporary interruptions and cases in which the start of the later cycle was deferred);
- Mean duration (in days) of interruptions to treatment by patient (declared duration of interruption or number of days delay identified for the start of the subsequent cycle);
- Reason for interruptions: Proportion of patients involved on at least one occasion for each of the reasons for interruption of treatment (AE, radiotherapy, surgery or other).

▪ **Description of permanent treatment discontinuations**

- Proportion of patients who discontinued sunitinib permanently;
- Reason for discontinuation: proportion of patients involved on at least one occasion for each of the reasons for discontinuation;
- Duration of treatment with sunitinib: time between starting sunitinib and the notified date to discontinue it or the date of the last consultation if sunitinib treatment was not stopped;
- Number of treatment cycles before discontinuation.

The analysis will be performed both on an overall basis and according to the number of calls made by the call center.

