9.4. Analysis of the primary end point

Table 30: Development of AEs during the follow-up period (safety population)

		Number of calls received < xx (N=xxx)	Number of calls received ≥ xx (N=xxx)	Call center (N=xxx)
At least 1 grade 3 or 4 AE whether or not related to Sunitinib	Yes	xx (xx%) [xx; xx]	xx (xx%) [xx; xx]	xx (xx%) [xx; xx]
	No	xx (xx%)	xx (xx%)	xx (xx%)
Number of grade 3 or grade 4 AEs, whether or not related to Sunitinib per patient	Number analyzed	xxx	xxx	xxx
	Mean (±SD)	xx (± xx)	xx (± xx)	xx (± xx)
	Median	xx	xx	xx
	Min-Max	xx - xx	xx - xx	xx - xx
Standardized grade 3 or 4 AEs, whether or not related to Sunitinib per patient, reported over the 6 months of treatment	Number analyzed	xxx	xxx	xxx
	Mean (±SD)	xx (± xx)	xx (± xx)	xx (± xx)
	Median	xx	xx	xx
	Min-Max	xx - xx	xx - xx	xx - xx

Table 31: Description of grade 3 and 4 AEs related or unrelated to sunitinib recorded during the follow-up period (safety population)

		Number of calls received < xx (N=xxx)	Number of calls received ≥ xx (N=xxx)	Call center (N=xxx)
Type of grade 3 or 4 AEs, whether or not related to Sunitinib (SOC – MedDRA category)*	xxxx	xx (xx%)	xx (xx%)	xx (xx%)
	xxxx	xx (xx%)	xx (xx%)	xx (xx%)
	xxxx	xx (xx%)	xx (xx%)	xx (xx%)
Type of grade 3 or 4 AEs, whether or not related to Sunitinib (PT – MedDRA category)*	xxxx	xx (xx%)	xx (xx%)	xx (xx%)
	xxxx	xx (xx%)	xx (xx%)	xx (xx%)
	xxxx	xx (xx%)	xx (xx%)	xx (xx%)

* Categories involving at least 2% of patients

These tables are described for patients under standard follow-up also for exploratory purposes.

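### The duration-adjusted AE rate in SAP 8.2.4 is a mean of per-patient ratios that a few early stoppers can dominate; a pooled rate should stand beside it and the formula's missing bracket be restored

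*SAP*

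**What the plan says.** SAP 8.2.4 lists one item under its sensitivity heading. It is meant to show whether the primary result depends on how long patients were treated. Each patient receives a grade 3/4 AE rate expressed over 6 months of treatment, defined as "the number of events which occurred/number of treatment months with sunitinib/ 6". A closing bracket follows and has no partner.

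Events are counted to the end of cycle 4, or "until the treatment is stopped if it is discontinued in the 1st, 2nd or 3rd cycle". The analysis uses the safety population, defined in SAP 5.1 as "Patients treated with Sunitinib", with no minimum exposure.

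The result appears in Table 30 (SAP 9.4) in the row "Standardized grade 3 or 4 AEs, whether or not related to Sunitinib per patient, reported over the 6 months of treatment". That row shows number analyzed, mean (SD), median and min-max, overall and in two columns split by calls received. It has no row of total events over total treatment time.

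Section 8.2.4 does not define treatment months. SAP 8.2.5.1 defines treatment duration as "time between starting sunitinib and the notified date to discontinue it or the date of the last consultation if sunitinib treatment was not stopped", which need not end when the event window ends.

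**The concern.** There are two separate matters.

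**The formula.** Read from left to right, the printed text divides by 6 where it should multiply by 6. This is a slip in the text and should be corrected before programming.

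**The summary.** A ratio with a very short denominator becomes very large after a single event. Averaging such ratios gives every patient equal weight, however short the exposure, so the mean and SD can be set by two or three people. If grade 3/4 AEs lead some patients to stop early, the mean in one call column could be far above the other while events per treatment month barely differ. Toxicity is a listed reason for stopping in Table 36, but the documents do not say how often it occurs.

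The low-call column is where this would show. SAP 5.2 requires a minimum "representing at least 3 calls in each of the first two cycles", and under Protocol 8.2, after a stop, "the call following termination will close the intervention". A patient who stops in cycle 1 therefore cannot enter the high-call column.

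**Working it through.** The plan gives no figure for this row, so there is nothing of its own to reproduce. Its one precision figure, 1.96 x sqrt(0.5 x 0.5/100) = 9.8 points, is correct but concerns the primary proportion.

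**Inputs from the documents.** Four cycles of 6 weeks = 168 days. Sample size 100. For the background risk, Protocol 6.1.2 reports that in a French real-life study "58% of patients treated with sunitinib presented with at least one grade 3 or 4 adverse event"; it gives 84% for the pivotal trial.

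**Assumptions.** A month is 30.4375 days. The 58% is treated as a 24-week risk at a constant rate, although the protocol states no time window for it. The low-call column has 20 patients, of whom 3 stop early. The documents give neither number, nor any stop times.

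**Step 1: the bracket.** For 2 events in 6 months, 2/(6/6) = 2.0; read literally, 2/6/6 = 0.056. The factor is 36.

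**Step 2: score of one event, 6 / months.**

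| Treatment stops at | Months | Score |
|---|---|---|
| day 7 | 0.230 | 26.1 |
| day 14 | 0.460 | 13.0 |
| day 28 | 0.920 | 6.5 |
| day 42 | 1.380 | 4.3 |
| day 168 | 5.520 | 1.09 |

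**Step 3: underlying rate.** -ln(1 - 0.58) = 0.868 events per 24 weeks. Then 0.868/5.520 = 0.157 per month, or 0.943 per 6 months.

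**Step 4: mean against pooled rate.** With N patients, 3 early stoppers treated for t months, and j of them having one event:

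- mean = (j x 6/t + (N - 3) x 0.943) / N
- pooled = 6 x (j + (N - 3) x 0.868) / (3t + (N - 3) x 5.520)

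For N = 20, day 14, j = 3: mean = (3 x 13.04 + 17 x 0.943)/20 = 2.76; pooled = 6 x (3 + 17 x 0.868)/(3 x 0.460 + 17 x 5.520) = 1.12.

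| Setting | Mean, j = 0 to 3 | Pooled, j = 0 to 3 |
|---|---|---|
| N = 20, stops at day 14 | 0.80 to 2.76 | 0.93 to 1.12 |
| N = 20, stops at day 42 | 0.80 to 1.45 | 0.90 to 1.09 |
| N = 100, stops at day 14 | 0.91 to 1.31 | 0.94 to 0.97 |
| N = 20, day 14, background 84% | 1.69 to 3.65 | 1.96 to 2.15 |

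**Step 5: stopping unrelated to AEs, constant rate.** Mean and pooled rate both have expectation 0.94. For N = 20 and day 14, the SD over repeats is sqrt(36/400 x (3 x 0.157/0.460 + 17 x 0.157/5.520)) = 0.37 for the mean and sqrt(36 x 0.157/(3 x 0.460 + 17 x 5.520)) = 0.24 for the pooled rate. The mean is noisier but not biased.

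**Step 6: stopping unrelated to AEs, events front-loaded.** Let the cycle 1 rate be twice the later rate r per day, with the same 24-week total: 42 x 2r + 126 x r = 210r = 0.868, so r = 0.00413. Expected events by day 14 are 14 x 2 x 0.00413 = 0.116, an expected score of 1.51. The mean is (3 x 1.51 + 17 x 0.943)/20 = 1.03; the pooled rate is 6 x (3 x 0.116 + 17 x 0.868)/(3 x 0.460 + 17 x 5.520) = 0.95, against 0.94 over full treatment. The mean can therefore be too high even when AEs do not cause stopping.

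**The case against.** The case for leaving the SAP as it is has real weight.

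- The phrase about 6 months leaves one sensible reading of the formula, and the lost bracket may come from the text extraction. Alone it is clerical. This stands.
- A patient-weighted mean and an exposure-weighted rate are different summaries, and the pooled rate gives little weight to early stoppers, who may tolerate treatment least. This stands, and is why the pooled rate should supplement the per-patient figures.
- Table 30 already prints median and min-max, and min-max would expose extreme ratios. A reader can approximate a pooled rate as 6 x mean events (Table 30) / mean duration (Table 36). This stands for the point estimate, provided both rows cover the same patients and window; a confidence interval cannot be recovered that way.
- The plan has no tests and no decision rules (SAP 4.1 and 4.2), so no formal conclusion hangs on this row. This stands and limits the severity.
- The number and timing of early stops are assumed, and the effect shrinks if stops come at the first planned visit. An event need not mean an immediate permanent stop: the nurse script (Protocol Appendix 7, D.5) provides for temporary interruption pending the oncologist's opinion. This stands; hence the day 42 figures above.

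A reader might also infer that the median is no safer. At 58% with 3 of 20 stopping at day 14 and stopping unrelated to AEs, the median is 0 in about 39% of repeats, but at 84% in only 0.2%. The documents do not support a general claim against the median.

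**Conclusion.** The point holds as a minor one. The formula needs its bracket, and the mean of per-patient ratios is a fragile summary for an analysis whose purpose is to account for treatment duration. In a call column of 20 with 3 stops at day 14, the mean can vary by a factor of about 3.4 (2.76/0.80) with the number of those three who have an event; the pooled rate varies by about 1.2 (1.12/0.93). For stops at day 42 the factors are about 1.8 and 1.2, and for all 100 patients with day-14 stops about 1.4 and 1.03. All of this rests on assumed stop numbers, stop times and event rates.

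Three stronger readings are not supported. First, the mean is not necessarily biased: it is too high if AEs cause stopping or are concentrated early in treatment, and otherwise only more variable. Second, the primary proportion is not affected by this row. Third, a pooled rate would not make the call columns comparable. Cycle 1 stoppers fall in the low-call column by definition whichever summary is used, so a difference between columns in this row should not be read as an effect of the calls.

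**What to change.** In SAP 8.2.4, write: rate per patient = 6 x number of grade 3/4 AEs / number of treatment months. State that treatment months cover the same window as the counted events, from the start of sunitinib to treatment stop or the end of cycle 4.

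In Table 30, add for each column: pooled rate = 6 x total grade 3/4 AEs / total treatment months. Show both totals and a 95% CI that allows for repeated events within a patient, for example a bootstrap by patient. Keep the per-patient median and range. Add a footnote that the pooled rate gives little weight to patients who stop early, and that the call columns should not be compared as an effect of calls on this row.

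The cost is one corrected formula, one table row and one footnote. No new data are needed, because event counts and treatment duration are already planned outputs (Tables 30 and 36).

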One adverse event led to hospitalisation in 35% of patients. The main grade 3 events that led to hospitalisation were anaemia (22 patients, 7.3%), deterioration of general condition (10 patients, 3.3%), hypertension (7 patients, 2.3%), fatigue/asthenia (6 patients 2.0%) and a cardiovascular event (6 patients, 2.0%). 65% of patients with at least one dose reduction, 61.6% of patients with at least one cycle postponement.

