8.5. Complete population justification (physicians/patients)

The patients included in this study will receive support from a therapy management platform in addition to usual follow-up by their oncologist.

The estimated number of patients (n) is determined by the precision (i) required when estimating the proportion (p) of patients presenting with at least one grade 3 or 4 AE. A 95% confidence interval is associated with the estimation of this proportion. The smaller the amplitude of this confidence interval, the greater the precision. Precision is given by the following formula:

$$i = 1.96 \sqrt{\frac{p(1-p)}{n}}$$

Depending on the observed proportion and on the size of the studied population, the following precision levels may be achieved:

Observed proportion	Resulting precision		
	n=75	n=100	n=125
10 – 90	6.8	5.9	5.3
20 – 80	9.1	7.8	7.0
30 – 70	10.4	9.0	8.0
40 – 60	11.1	9.6	8.6
50	11.3	9.8	8.8

Precision is minimum where the amplitude of the maximum confidence interval for a given proportion is equal to 50%. Failing any hypothesis concerning the value of the expected proportion, the hypothesis of a 50% proportion will be used. Thus, we can show that 100 patients will need to be included to estimate a percentage with a 95% confidence interval whose amplitude does not exclude $\pm 9.8\%$.

Between 10 and 20 centres are expected to participate in France, that shall each include 10 patients on average.

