The therapeutic management of patients within the facility will not be changed by the study and will follow the recommendations in the SmPC. Patients who are included will receive an additional intervention with follow-up from the treatment management telephone call center. Management through the treatment management telephone call center involves regular telephone calls (cf. Figure 1) in order to support the patient in his/her home management with sunitinib treatment under real life conditions (prevention, advice and directing patients towards options available).

[figure not shown]

Figure 1. Plan of telephone calls

■ **Populations**

- **Population of Participating doctors**

The study will be proposed to 58 doctors throughout 50 Mainland France oncology centers identified as treating patients suffering from metastatic/advanced renal cell carcinoma. It is planned to identify 20 to 25 doctors liable to take part in the study.

These centers will be selected by the Pfizer Company. They will need to have a number of patients which meet the eligibility criterion which is sufficient to be included (approximately 10 patients per year) and not to have a routine management call center already in place in their facility.

- **Patient Population**

It is expected to recruit 100 patients for this study, i.e. approximately 10 per center. The patients must meet the following inclusion and non-inclusion criteria.

Table 1: Patient eligibility criteria

Inclusion criteria	Non-inclusion criteria

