3. INTERIM ANALYSIS AND FINAL ANALYSIS

No interim analysis is planned.

The **final data analysis** will be performed following the data collection and after freezing the database as approved with Pfizer. After the amendment to the protocol (no. 3.1), it was agreed that the statistical analyses be performed on all patients who were followed up by the telephone “Call Center” platform.

Patients initially included in the “standard follow-up” group will be described for informative purposes from their major characteristics at inclusion and during follow-up.

A final statistical report will describe all of the planned analyses in the SAP and any additional analyses requested. This statistical report will not contain any description or comment about the results.

A study report will be written and submitted to Pfizer. This document will provide a discussed overview of the results of the analyses in order to meet the objectives of the study.

The results of the RENACALL study may be discussed in terms of the results of the SANTORIN study [8].

The reports will be written in French.

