9.6. Pharmacovigilance

Note: The pharmacovigilance analysis will be described both according to severity (AE/SAE) and overall.

Table 54: Description of all of the AEs declared during the study (Safety population)

		Safety population (N=xxx)
Type of AEs (SOC – MedDRA category)*	xxxx	xx (xx%)
	xxxx	xx (xx%)
	xxxx	xx (xx%)
Type of AEs (PT – MedDRA category)*	xxxx	xx (xx%)
	xxxx	xx (xx%)
	xxxx	xx (xx%)
cycle	cycle 1	xx (xx%)
	cycle 2	xx (xx%)
	cycle 3	xx (xx%)
	cycle 4	xx (xx%)
Severity	Non-serious	xx (xx%)
	Serious	xx (xx%)
If serious, severity criteria	Fatal	xx (xx%)
	Life-threatening	xx (xx%)
	Hospitalization/prolongation of hospitalization	xx (xx%)
	Congenital abnormality/ malformation	xx (xx%)
	Permanent or severe invalidity/ incapacity	xx (xx%)
	Significant medical event	xx (xx%)
Grade	1	xx (xx%)
	2	xx (xx%)
	3	xx (xx%)
	4	xx (xx%)
	5	xx (xx%)
	Not applicable	xx (xx%)
Causality of the AEs with sunitinib	Related to administration of Sutent®	xx (xx%)
	Related to a concomitant medicinal product	xx (xx%)
	Related to Sutent and another concomitant medicinal product	xx (xx%)
	Related neither to Sutent nor another medicinal product	xx (xx%)
	Unknown	xx (xx%)
Outcome	Recovered	xx (xx%)
	Recovered with sequelae	xx (xx%)
	Currently recovering	xx (xx%)
	Not recovered	xx (xx%)
	Unknown	xx (xx%)
Corrective medical action	Prescription of a treatment	xx (xx%)
	Medical consultation	xx (xx%)
	Hospitalization	xx (xx%)
	Other	xx (xx%)
	Not applicable	xx (xx%)
Last action undertaken for Sutent during the AE	Discontinuation (temporary or permanent, or dose delayed)	xx (xx%)
	Increased dosage	xx (xx%)
	Reduced dosage	xx (xx%)
	Unchanged dosage	xx (xx%)

		Safety population (N=xxx)
	Change in dosage regimen	xx (xx%)
	Unknown	xx (xx%)
	Not applicable	xx (xx%)
Specific situation	No specific situation	xx (xx%)
	Exposure during pregnancy	xx (xx%)
	Overdose	xx (xx%)
	Medication error/Risk of medication error	xx (xx%)
	Exposure during breast-feeding	xx (xx%)
	Misuse	xx (xx%)
	Lack of efficacy	xx (xx%)
	Off-label use	xx (xx%)
	Extravasation	xx (xx%)
	Occupational exposure	xx (xx%)

* Categories involving at least 2% of patients

Table 55: Description of all AEs related to sunitinib declared during the follow-up period (Safety population)

		Safety population (N=xxx)
AEs related to sunitinib*		
Type of AE (SOC – MedDRA category)**	xxxx	xx (xx%)
	xxxx	xx (xx%)
	xxxx	xx (xx%)
Type of AE (PT – MedDRA category)**	xxxx	xx (xx%)
	xxxx	xx (xx%)
	xxxx	xx (xx%)
Cycle	cycle 1	xx (xx%)

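### The 2% display rule leaves rare grade 3/4 and serious adverse event terms unnamed in the SOC/PT summary rows, which conflicts with SAP 8.2.6; they are counted in aggregate rows and reliably named only in annex listings

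*SAP*

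**What the plan says.** SAP 8.2.4 plans, as a secondary analysis of the primary end point, the incidence of the main grade 3 or 4 adverse events by SOC and PT, and adds: "Only categories involving at least 2% of patients will be presented". The footnotes of Table 31 (grade 3/4 events), Table 54 (all events) and Table 55 (sunitinib-related events) carry the same limit: "Categories involving at least 2% of patients". In each table the asterisk sits on the SOC and PT rows only.

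The note that opens SAP 9.6 says: "The pharmacovigilance analysis will be described both according to severity (AE/SAE) and overall". SAP 8.2.6 likewise asks for its indicators for all, non-serious and serious events. Neither section exempts serious events from the limit. Yet 8.2.6 also promises to describe every declared event by its coded MedDRA title and states no threshold.

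On the denominator, SAP 2.2 says: "It is expected to recruit 100 patients for this study, i.e. approximately 10 per center". SAP 5.1 defines the safety population as "Patients treated with Sunitinib". That includes the patients of the discontinued arm, of whom SAP 3 says: "Patients initially included in the “standard follow-up” group will be described for informative purposes". SAP 5.1 wants the two subgroups kept apart wherever applicable, but Tables 54 and 55 have one undivided safety-population column.

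**The concern.** A 2% cut-off is a common way to shorten a table of mild events. Here the same cut-off covers grade 3/4 events and, as the text stands, serious and fatal ones, in a study of about 100 patients whose primary end point is grade 3/4 events. A reader of the summary tables could find one fatal or one grade 4 event counted in an aggregate row, with no SOC or PT row saying what it was. A term missing from the list could also be taken to mean that no such event occurred.

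Two further gaps make the display harder to read. The SAP does not say which denominator the 2% refers to. And the single column of Tables 54-55 mixes patients who received the calls with patients who did not.

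**Working it through.** **Planned size.** Protocol 8.5 uses i = 1.96 × √(p(1 − p)/n). With p = 0.5 and n = 100, i = 1.96 × √(0.25/100) = 0.098, which reproduces the stated ±9.8 points. So N = 100 is the planned figure. The number actually analysed, and the number of standard follow-up patients, are not in the documents.

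**What the rule hides.** A category with k patients is dropped when k/N < 0.02, that is, when 50k < N.

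| N in the denominator | Largest count not shown | Check |
|---|---|---|
| up to 50 | 0 | 1/50 = 2.0%, shown |
| 51 to 100 | 1 | 1/51 = 1.96% and 1/100 = 1.0%, dropped; 2/100 = 2.0%, shown |
| 101 to 150 | 2 | 2/101 = 1.98% and 2/150 = 1.33%, dropped; 3/150 = 2.0%, shown |
| from 151 | 3 | 3/151 = 1.99%, dropped |

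**How often this matters.** Let X be the number of patients with a given term, binomial (N, p), and h the largest count not shown. The chance that the term occurs but is not named is P(1 ≤ X ≤ h). The true rates p are assumptions.

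- N = 100, h = 1, p = 0.02: 100 × 0.02 × 0.98^99 = 0.271
- N = 100, h = 1, p = 0.01: 100 × 0.01 × 0.99^99 = 0.370

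The same calculation over a range:

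| N (h) | p = 0.5% | p = 1% | p = 2% | p = 3% |
|---|---|---|---|---|
| 75 (1) | 26% | 36% | 34% | 24% |
| 100 (1) | 30% | 37% | 27% | 15% |
| 101 (2) | 38% | 56% | 54% | 37% |
| 125 (2) | 44% | 58% | 46% | 25% |

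Only N = 100 comes from the plan as expected enrolment. The other rows show the effect of a different, unknown N.

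**Where the event still appears.** Table 30 counts every patient with a grade 3/4 event and the number of such events. Table 54 has unfiltered rows for seriousness, seriousness criterion (including fatal), grade 1 to 5, causality and outcome; Table 55 has the same rows for sunitinib-related events. A SOC row survives if other events bring that SOC to 2%. Table 28 gives broad, ungraded symptom groups for Call Center patients. Table 36 gives details of toxicity that ended treatment, and a row for deaths. SAP 8.2.7 plans annex listings of patients with adverse and serious adverse events. What is lost is the named PT row, and sometimes the SOC row.

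**Unstated denominator.** Table 31 has two call-count columns and a Call Center total, and is to be repeated for standard follow-up patients. If the rule is applied within each group, a single case is named in a group of 50 or fewer and dropped in a group of 51 to 100. The same event could then be named in one group and absent in another.

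**The case against.** The strongest reply is that this concerns layout only. Section 8.2.4 announces the *main* grade 3/4 events, so Table 31 never promised a full list. The aggregate rows are complete, and the listings name each event. Under Protocol section 10 every serious event is recorded and reported to the sponsor within 24 hours, so surveillance does not depend on these tables. No estimate changes. All of this stands, and it makes the case for Table 31 the weaker one.

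It is also fair to say that no shell for the serious-event version is printed. That the filter reaches it follows from the footnote, the note in 9.6 and the lack of an exemption, while the text of 8.2.6 points the other way. This is a conflict to be settled, not an explicit rule to hide serious events.

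Three stronger readings are tempting but not supported:

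- A reader might infer that a rare severe event vanishes from all safety output. It does not, as the aggregate rows and listings show.
- A reader might infer that pooling pushes N above 100, so that terms with two patients are lost and the chances exceed one half. The documents do not say how many standard follow-up patients there are, or whether they fall within the 100. Table 31's total column is Call Center only.
- A reader might take the rates of 2.0% to 2.3% in Protocol 6.1.2 (cardiovascular events, fatigue/asthenia, hypertension) as showing that Table 31 would lose such events. Those are grade 3 events that led to hospitalisation, so they bear only on the serious-event tables. The same section gives 12.6% for grade 3 hypertension and 11.9% for grade 3 fatigue/asthenia. At 11.9% and N = 100 the chance of going unnamed is 100 × 0.119 × 0.881^99, about 0.00004. A cardiovascular event is also a broad class, not a preferred term.

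What the reply does not answer is that the listings are an annex to a statistical report that, under SAP 3, carries no commentary, while the discussed results go into a separate study report. A listing gives neither counts nor percentages by term.

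**Conclusion.** The point holds as one of incomplete naming. Under the rule as written, a grade 3/4 or serious term seen in one patient (N = 51 to 100), or in up to two (N = 101 to 150), is not named in the SOC/PT rows. At the planned 100 patients this has a 27% chance for a term with a true rate of 2%, and 37% for one at 1%. These figures assume those rates, independent patients and an overall denominator of 100. The case is strongest for the serious-event versions of Tables 54-55, where the footnote also conflicts with 8.2.6, and weaker for Table 31. The correction is a cheap improvement to safety reporting and leaves the primary estimate unchanged.

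**What to change.** 1. In the serious-event versions of Tables 54-55, show every SOC and PT with at least one patient, including grade 5 events. Do the same for the grade 3/4 events in Table 31.
2. Keep the 2% limit only for terms whose reported events are all non-serious and grade 1 or 2. State its denominator.
3. Reword 8.2.6, 9.6 and the footnotes so that the commitment to describe all events by MedDRA term and the display limit agree.
4. Give Tables 54-55 separate Call Center and Standard follow-up columns, in line with SAP 5.1.

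The cost is some SAP wording and longer tables. No new data are needed.
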